### 11.8.3 ADVERSE EVENTS

Six months after the first subject is enrolled in the study, and at the end of each 6 months thereafter, a semi-annual statistical analyses and review of all AEs will occur. The SDMC will:

- Use the current version of the MedDRA dictionary to code all AEs that have been recorded on study AE forms.
- Make a “snapshot” copy of the AE data, including MedDRA codes.
- Create frequency tables of treatment x occurrence (yes or no, since inception of the study) of all patients. One table will be created for each highest-level MedDRA term for which AEs have been reported. The counting units are patients, not events.
- Compute the FET statistic to test the alternative hypothesis that occurrence of AEs is not independent of treatment group. The FET p-value is not adjusted for multiplicity.
- If the FET p-value is less than the critical value shown in Table 11.3 and the active treatment group has a higher AE rate, the SDMC will conduct further statistical analyses as indicated by the circumstances and alert the DSMB to this finding in the semi-annual DSMB report.
- Collaborate with the Principal Investigator to incorporate the results into the study’s semi-annual report to the DSMB and the NHLBI Project Officer.

### 11.8.4 TRANSFUSION REACTIONS

Six months after the first subject is enrolled in the study, and at the end of each 6 months thereafter, a semi-annual statistical analyses and review of all transfusion reactions will occur, regardless of the incidence rates. The SDMC will create a report that consists of:

- Development of clinically significant alloantibodies
- Development of autoantibodies associated with hemolysis that results in the inability to transfuse safely.
- Development of clinically significant hemolytic transfusion reactions.

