If > 1 year has passed since the subject's participation in Phase I (or if the subject was not enrolled in Phase I), the subject must complete the MMSE and the POMS, as well as the WAIS-III PIQ portion of the Neuropsych Battery to confirm eligibility. If eligible, the study coordinator will complete the screening blood draw and schedule an MRI to be completed at Visit 2. (For subjects enrolled in Phase I, this is a repeat MRI that should be compared to the Phase I MRI to confirm there are no new neurological findings. If eligible to continue, the subject will return for Visit 3, during which the SF-36 and the remainder of the Neuropsych Battery is administered and the subject is randomized.

Patients randomized to the transfusion arm will receive six to eight transfusions over the course of six months. The first transfusion must occur within 2 weeks of randomization. The specific method of randomization is described in greater detail in the Statistical Analysis section of the protocol and the Study Information Manual for this study. The goal is to maintain a minimum of at least 2 g/dL rise of Hb over the baseline. Once transfusions are started, the pre-transfusion Hb obtained within three days of the transfusion should be 9.0 g/dL or greater, without exceeding a post-transfusion Hb concentration of 12.0 g/dL. All transfusions will be leukodepleted and Hb S negative. Phenotypically matched red blood cells for D, C/c, E/c, and Kell1 antigens are required, along with any known antibody. Only simple transfusion will be allowed. Simple transfusion guidelines include the maximum delivery of 3.0 units of packed red blood cells (RBCs) per transfusion at 3-4 week intervals. Prior to each transfusion, an interval history form will be completed and women of childbearing potential will be asked whether they suspect they might be pregnant. If the answer is "Yes" or "Not Sure," a urine sample will be collected and a pregnancy test will be performed.

Patients randomized to the standard care arm will follow their normal care regimen, and will be asked to complete, on a monthly basis, an interval history form noting any new medications, neurological events, transfusions, hospitalizations, etc. the patient may have had since the last interval history. The interval history will be conducted via telephone during Months 1, 2, 4, and 5. During Months 3 and 6, the patient will make in-person

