## 11.8 SUSPENSION GUIDELINES

### 11.8.1 OVERVIEW

SAEs, AEs, and abnormal laboratory measures will be monitored quarterly throughout the study and if a significant imbalance between the two treatment groups in any of these measures is observed, the DSMB and NHLBI will be notified immediately to consider a suspension of enrollment into the study. This section details the process for assessing imbalances in these measures.

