Transfusion Reactions	The SDMC will report the following events semi-annually to the DSMB, regardless of incidence rates: 
 
• Development of clinically significant alloantibodies
 
• Development of autoantibodies associated with hemolysis that result in inability to transfuse safely.
 
• Development of clinically significant hemolytic transfusion reactions.
 
	Report all cases	Semi-annual
Clinical Laboratory Results	
 
• SDMC performs semi-annual analyses of clinical laboratory (hemoglobin and ferritin) change-from-baseline data for each clinical laboratory evaluation obtained in this study.
 
	Report all cases	Semi-annual

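### Section 11.8.1 promises quarterly safety monitoring with immediate notice of an imbalance, but the operative sections set AE and laboratory review at six months; transfusion reactions share that cycle, which is as long as the transfusion course.

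*Protocol*

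**What the plan says.** **The general commitment.** Section 11.8.1 opens the suspension guidelines with "SAEs, AEs, and abnormal laboratory measures will be monitored quarterly throughout the study". It continues: "if a significant imbalance between the two treatment groups in any of these measures is observed, the DSMB and NHLBI will be notified immediately", so that they can consider suspending enrollment.

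**The operative sections.**
- Adverse events, Section 11.8.3: every six months, "a semi-annual statistical analyses and review of all AEs will occur". If Fisher's exact test crosses the critical value with a higher rate on active treatment, the data center is to "alert the DSMB to this finding in the semi-annual DSMB report".
- Laboratory results, Section 11.8.5: hemoglobin and ferritin changes are analyzed every six months and go into the semi-annual report. No alert threshold is given.
- Transfusion reactions, Section 11.8.4: "a semi-annual statistical analyses and review of all transfusion reactions will occur, regardless of the incidence rates". The events are clinically significant alloantibodies, autoantibodies with hemolysis that prevent safe transfusion, and clinically significant hemolytic reactions. The fuller Table 11.3 in Section 11.9.1 agrees: "The SDMC will report the following events semi-annually to the DSMB, regardless of incidence rates".
- SAEs, Sections 11.7.3 and 11.8.2: analyzed quarterly. Outside the semi-annual report, they go to the DSMB only when Fisher's p < 0.01 and the active arm has the higher rate.
- Deaths, Section 11.7.3 and Table 11.3: to the DSMB within 15 calendar days.

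**The exposure.** Section 10.5: "Patients randomized to the transfusion arm will receive six to eight transfusions over the course of six months".

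**The concern.** Section 11.8.1 and the sections that carry it out give the data center different instructions on how often to look at AEs and laboratory results, and on what to do when an imbalance appears. One says quarterly with immediate notice. The others say every six months, with the notice held for the report.

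The difference matters more than usual here because the intervention lasts only six months. The board that recommends suspension may see a tabulation of intervention-specific harms only after patients who were on treatment when a signal arose have finished their course. Sites send every SAE to the data center by the end of the next business day (Section 11.7.1), so the delay lies in the step from data center to board, not in collection.

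**Working it through.** **1. The passages side by side**

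| Measure | Section 11.8.1 | Operative text |
|---|---|---|
| SAEs | Quarterly; immediate notice of imbalance | Quarterly, sent if p < 0.01 (11.8.2); all cases semi-annually |
| AEs | Quarterly; immediate notice of imbalance | Six-monthly; alert inside the semi-annual report (11.8.3) |
| Laboratory measures | Quarterly; immediate notice of imbalance | Six-monthly; no alert threshold (11.8.5) |
| Transfusion reactions | Not named | Six-monthly, all cases (11.8.4) |

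The direct contradiction is in the AE and laboratory rows. Transfusion reactions fall under Section 11.8.1 only in so far as they are also AEs, SAEs or abnormal laboratory measures. Table 11.3 appears twice. The version in Section 11.8.6 has no transfusion-reaction or laboratory row; the version in Section 11.9.1 has both, at six months.

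**2. Review interval against course**

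Inputs: a six-month course, taken as 26 weeks, and transfusions every 3 to 4 weeks (Section 10.5).

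- Per course: 26/4 = 6.5 and 26/3 = 8.7, in line with the protocol's 6 to 8.
- Between six-monthly reviews: up to the whole course, 6 to 8 transfusions.
- Between quarterly reviews (13 weeks): 13/4 = 3.25 and 13/3 = 4.3, so about 3 to 4 transfusions.

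These are maxima. Reviews run on calendar time from first enrollment and patients enter at different times, so only a patient who starts just after a cut goes the whole course between reviews.

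**3. How far the quarterly SAE route shortens the wait**

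Inputs: 36 randomized, 18 per arm, 30 expected to complete, 15 per arm (Section 13.1). The trigger is Fisher's exact p < 0.01 within one highest-level MedDRA term, counting patients (Section 11.8.2). With x patients affected on transfusion, none on standard care and n per arm, the two-sided value is

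p = 2 × C(n, x) / C(2n, x).

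- n = 18, x = 6: 2 × 18,564 / 1,947,792 = 0.019. No alert.
- n = 18, x = 7: 2 × 31,824 / 8,347,680 = 0.0076. Alert.
- n = 15: x = 6 gives 0.017 and x = 7 gives 0.0063, so the threshold is again 7.
- One control event at either size raises the requirement to 9 v 1.
- n = 4, early in enrollment: even 4 v 0 gives 2/70 = 0.029, so the trigger cannot fire.

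The protocol gives no expected event rates. Taking no control events, which favors the trigger, the chance that one look at full enrollment reaches x ≥ 7 is binomial:

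| Assumed active-arm rate | 18 per arm | 15 per arm |
|---|---|---|
| 10% | 0.1% | 0.03% |
| 20% | 5% | 2% |
| 30% | 28% | 13% |
| 40% | 63% | 39% |

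The route exists but will seldom bring a non-fatal SAE to the board early. Section 11.8.2 also contradicts itself about it: one bullet has the data center report when p is below the critical value, and another says no report is filed in that case.

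**4. The stop provision**

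Section 12.3 says that, apart from routine reports, the transfusion study stops pending DSMB consultation if occurrences described in Section 12 arise. Section 12 covers data collection and monitoring and lists none.

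**The case against.** The case on the other side has weight, and most of it limits how far the point can be taken.

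- **A reader might infer that every non-fatal harm waits six months.** It does not. A life-threatening reaction, or one needing hospitalization, is an SAE (Section 11.1.2) and enters the quarterly analysis. What remains is that the trigger is hard to reach.
- **A reader might infer that Section 11.8.1 promises immediate notice of each reaction.** It does not name transfusion reactions, and its immediate notice depends on a significant between-group imbalance. Section 11.8.4 therefore does not contradict it directly.
- **A reader might infer that patients are unprotected between reviews.** Antibody screening and hemoglobin measurement precede every transfusion (Section 10.6), an interval history is taken each time (Section 10.5), and investigators may discontinue a subject on safety grounds (Section 8.7). These protect the individual but do not inform the board.
- **Other routes are intended.** Section 11.7.3 opens by saying, without an interval, that safety issues will be brought to the DSMB, and Section 12.3 envisages a stop outside the periodic reports. Its pointer is probably a numbering slip for the safety section. The first has no trigger or time limit, and the second cannot be applied until the pointer is corrected.
- **Six months may be the intended interval.** It is stated consistently everywhere except Section 11.8.1, so the documents show that the two must be reconciled, not that quarterly was meant.
- **The Fisher result is partly a separate matter.** More frequent looks would not make p < 0.01 easier to reach with these numbers. It is relevant only because it shows how little the quarterly SAE route shortens the wait.

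**Conclusion.** The contradiction is real and lies in current operative text: Section 11.8.1 cannot be followed together with Sections 11.7.3, 11.8.3, 11.8.5 and Table 11.3 on AE and laboratory review or on the timing of an imbalance notice. It should be fixed.

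Separately, the six-monthly transfusion-reaction tabulation equals the course length. This is a weak design choice rather than a contradiction. The loss of a full course between reports is a worst case and depends on when a patient starts relative to the data cut. The seven-patient threshold assumes full enrollment, no control events and all events within one MedDRA term; the firing probabilities also rest on assumed event rates.

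The absence of individual expedited notice for non-fatal reactions is not an error in the plan, because nothing in the protocol promises it.

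**What to change.** 1. Reconcile Section 11.8.1 with Sections 11.7.3, 11.8.3 and 11.8.5 and with Table 11.3 wherever it appears. The preferable direction is to make the AE and laboratory reviews quarterly and to send an AE or laboratory imbalance alert when it is found, as Section 11.8.1 states.
2. Put the Section 11.8.4 tabulation, and its row in the fuller Table 11.3, on the same quarterly cycle.
3. Correct the reference to Section 12 in Section 12.3 so that it leads to the occurrences meant. Which occurrences those are is for the sponsor and the DSMB to state.

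The cost is protocol wording and about two extra tabulations a year for about 36 patients. The data center already receives SAE reports by the next business day, and no patient procedure is added.

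Optionally, the sponsor and the DSMB may consider individual expedited notice of non-fatal transfusion-specific SAEs. It would not depend on a between-group test that needs seven affected patients.

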### 11.8.5 CLINICAL LABORATORY RESULTS

Six months after the first subject is enrolled in the study, and at the end of each six months thereafter, a semi-annual statistical analyses and review of all clinical laboratory results will occur. The SDMC will:

- Make a “snapshot” copy of the study’s clinical laboratory data.
- Perform an appropriate statistical analysis of clinical laboratory (hemoglobin and ferritin) change-from-baseline data for each clinical laboratory evaluation obtained in this study.
- Collaborate with the PI to incorporate the results into the study’s semi-annual report to the DSMB and the NHLBI Project Officer.

### 11.8.6 PROCEDURES

This section specifies procedures for alerting the DSMB to serious safety issues that arise in this study. The incidences for alerting the DSMB are summarized in Table 11.3.

**TABLE 11.3 Summary of Procedures and Timing for Alerting the DSMB and NHLBI Project Officer of Possible Serious Safety Issues**

Situation or Event	Summary of Procedure (See text for details.)	Critical Value for DSMB “Alert”
SAEs reported with a SAE Criterion of Death	DSMB will be notified of all SAEs that are reported with a SAE criterion of Death within 15 days of the SDMC SAE Regulatory Specialist becoming aware of the event.	Death
SAEs (all)	1. SDMC performs quarterly analyses of MedDRA-coded SAEs, tabulates patients with SAEs classified by highest level MedDRA term. Report only when $p < \text{critical value}$ and active treatment group has higher AE rate. 2. SDMC performs semi-annual analyses of MedDRA-coded SAEs, tabulates patients with SAEs classified by highest level MedDRA term.	$p < 0.01$ $p$ not adjusted for multiplicity
AEs (all)	SDMC performs semi-annual analyses of MedDRA-coded AEs, tabulates patients with AEs classified by highest level MedDRA term. Report every six months. Alert only when FET $p < \text{critical value}$ and active treatment group has higher AE rate.	$p < 0.01$ $p$ not adjusted for multiplicity

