### 11.8.2 SERIOUS ADVERSE EVENTS

Three months after the first patient is enrolled in the study, and at the end of each three months thereafter, a quarterly statistical analyses and review of all SAEs will occur pending there have been SAEs reported during these timeframes. The SDMC will:

- Use the current version of the MedDRA dictionary to code all SAEs that have been recorded on study AE case report forms.
- Make a “snapshot” copy of the SAE data, including MedDRA codes.
- Create frequency tables of treatment x occurrence (yes or no, since inception of the study) of all patients. One table will be created for each highest level MedDRA term for which SAEs have been reported. The counting units are patients, not events.
- Compute Fisher’s Exact Test (FET) statistic to test the alternative hypothesis that occurrence of SAEs is not independent of treatment group. The FET p-value is not adjusted for multiplicity.
- If the FET p-value is less than the critical value shown in Table 11.3 and the active treatment group has a higher SAE rate, the SDMC will conduct further statistical analyses as indicated by the circumstances and report the results to the Chair of the DSMB subcommittee monitoring this study, the PI, and the NHLBI Project Officer.
- The SDMC will not file a report to the DSMB and the NHLBI Project Officer if the FET p-values is less than the critical value shown in Table 11.3.
- On a semi-annual basis the DSMB and the NHLBI Project Officer will receive a semi-annual report of all the SAEs reported regardless if a quarterly report was administered because a data trigger was found.

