## 11.9 REPORTS TO THE DSMB, STUDY INVESTIGATORS, IRBS, AND OTHER AUTHORITIES

### 11.9.1 SERIOUS ADVERSE EVENTS

The site investigator, the Principal Investigator, and the SDMC SAE Regulatory Specialist will collaborate to prepare a MedWatch 3500A report for any SAE that is fatal. The Principal Investigator will submit the report to (a) the Chair of the DSMB

Subcommittee appointed to monitor this study and to (b) the NHLBI Project Officer within 15 calendar days of initial notification to the SDMC SAE Regulatory Specialist.

If a safety signal is detected, a Dear Investigator Letter will be sent via the SDMC to all site study investigators. Each study investigator will submit the SAE report to the local IRB in accordance with the institution's regulations.

**TABLE 11.3 Summary of Procedures and Timing for Alerting the DSMB and NHLBI Project Officer of Possible Serious Safety Issues**

Situation or Event	Summary of Procedure (See text for details.)	Critical Value for DSMB "Alert"	Frequency
SAEs reported with a SAE Criterion of Death	DSMB will be notified of all SAEs that are reported with a SAE criterion of Death within 15 days of the SDMC SAE Regulatory Specialist becoming aware of the event.	Death	15 calendar days from SDMC notification
SAEs (all)	SDMC performs quarterly analyses of MedDRA-coded SAEs, tabulates patients with SAEs classified by highest level MedDRA term. Report only when $p < \text{critical value}$ and active treatment group has higher AE rate.	$p < 0.01$ $p$ not adjusted for multiplicity	Quarterly if meets critical alert value
SAEs (all)	SDMC performs semi-annual analyses of MedDRA-coded SAEs, tabulates patients with SAEs classified by highest level MedDRA term.	Report all cases	Semi-annual
AEs (all)	SDMC performs semi-annual analyses of MedDRA-coded AEs, tabulates patients with AEs classified by highest level MedDRA term. Report every six months. Alert only when FET $p < \text{critical value}$ and active treatment group has higher AE rate.	$p < 0.01$ $p$ not adjusted for multiplicity	Semi-annual if meets critical alert value

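### Table 11.3 ties the quarterly SAE alert to a higher AE rate on the active arm, whereas section 11.8.2 requires a higher SAE rate; read literally, the table could delay an alert

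*Protocol*

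**What the plan says.** The quarterly SAE rule is stated in three places in the Protocol.

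- **Section 11.8.2 (text).** One frequency table is made per highest-level MedDRA term, and "The counting units are patients, not events". Fisher's exact test addresses the alternative that "occurrence of SAEs is not independent of treatment group". The reporting bullet reads "If the FET p-value is less than the critical value shown in Table 11.3 and the active treatment group has a higher SAE rate", after which the SDMC analyses further and informs the DSMB subcommittee chair, the PI and the NHLBI Project Officer.
- **Section 11.8.6, Table 11.3 (first printing).** The row for all SAEs "tabulates patients with SAEs classified by highest level MedDRA term", but its direction condition is "and active treatment group has higher AE rate. 2. SDMC performs semi-annual analyses of MedDRA-coded SAEs".
- **Section 11.9.1, Table 11.3 (second printing).** The quarterly SAE row again says "and active treatment group has higher AE rate".

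The critical value is p < 0.01, unadjusted. Section 11.7.3 points to Table 11.3 for what triggers a DSMB review of the quarterly SAE data.

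The bullet in 11.8.2 directly after the reporting bullet says that no report is filed with the DSMB and the Project Officer when the Fisher p-value is below the critical value. That is the opposite of the bullet before it.

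**The concern.** The AE rate and the SAE rate are different quantities. An excess of serious events on transfusion can coexist with equal AE rates if most patients in both arms have at least one AE of some kind. The Protocol makes that plausible. Its AE definition includes exacerbations of pre-existing conditions, events attributed to sickle cell disease must still be recorded (11.5), and Table 11.2 lists pain, fever and anemia among the expected AEs.

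Of the analyses described in 11.8.2 to 11.8.5, only the SAE test is scheduled quarterly; the others are semi-annual. A direction condition on the wrong variable therefore weakens the one scheduled statistical check that could bring a non-fatal signal to the DSMB between semi-annual reports.

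**Working it through.** **Side by side**

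| Place | Tested | Direction condition |
|---|---|---|
| 11.8.2, reporting bullet | patients with SAEs | higher SAE rate, active arm |
| Table 11.3 in 11.8.6, SAE row | patients with SAEs | higher AE rate, active arm |
| Table 11.3 in 11.9.1, quarterly SAE row | patients with SAEs | higher AE rate, active arm |
| Table 11.3, AE row (both printings) | patients with AEs | higher AE rate, active arm |

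The SAE row carries the same condition as the AE row. The Protocol gives no alert probability for this rule, so there is no stated figure to reproduce.

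**A single example**

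Inputs: 36 patients randomized (section 13.1), hence 18 per arm; critical value 0.01 (Table 11.3). The test is taken as two-sided, because the alternative is non-independence and direction is checked separately. The event counts are chosen for illustration.

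SAEs in 9 of 18 v 1 of 18, so 10 patients with SAEs among 36:

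- P(9 on active) = C(18,9) × C(18,1) / C(36,10) = 48,620 × 18 / 254,186,856 = 0.00344
- P(10 on active) = C(18,10) / C(36,10) = 43,758 / 254,186,856 = 0.00017
- One tail = 0.0036. The arms are equal in size, so the two-sided p = 2 × 0.0036 = 0.0072, below 0.01.

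Suppose every patient has some AE, 18 v 18. The rule in 11.8.2 gives an alert, since 9/18 exceeds 1/18. The rule in Table 11.3 gives none, since 18/18 does not exceed 18/18.

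**How often this could happen, under assumed rates**

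The Protocol gives no AE or SAE rates, so all rates here are assumptions. The simulation used 20,000 runs per scenario, 18 per arm, and SAEs in a single table rather than split by MedDRA term. A patient has an AE if they have an SAE or an independent non-serious event with probability q, the same in both arms. A trigger is Fisher p < 0.01 with more SAEs on active. It is blocked if the active AE count is tied or lower.

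| q | Blocked, SAE 50% v 10% | Blocked, SAE 60% v 10% |
|---|---|---|
| 30% | 0.8% | 0.3% |
| 50% | 4.9% | 2.8% |
| 80% | 23.7% | 20.1% |
| 90% | 39.0% | 36.4% |
| 95% | 54.9% | 53.1% |
| 100% | 100% | 100% |

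Triggers occurred in about 40% and 64% to 65% of runs respectively.

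**Under the 11.8.2 condition**

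Direction is judged on the counts that are tested. With 18 per arm the alert starts at 7 v 0 (p = 0.0076), 9 v 1 (p = 0.0072) or 11 v 2 (p = 0.0045). With 15 per arm, the expected completers, it starts at 7 v 0 (p = 0.0063), 9 v 1 (p = 0.0052) or 10 v 2 (p = 0.0078). The AE rate plays no part.

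**The case against.** The strongest reply is that the text already settles the matter. Both printings head the procedure column as a summary and send the reader to the text, and 11.8.2 takes only the critical value from the table and states the direction itself: "and the active treatment group has a higher SAE rate". The SAE row tabulates only patients with SAEs, and the quarterly data snapshot in 11.8.2 is of SAE data, while AE tables are specified every six months in 11.8.3. The phrase matches the AE row, so a copying slip is more likely than a deliberate rule on another variable. Section 11.8.1 also calls for immediate notification of a significant imbalance in SAEs, with no AE condition.

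Most of this stands, and it limits the seriousness of the point. It does not remove it. Section 11.7.3 names Table 11.3 as the source of the quarterly trigger, the error is in both printings, and the text to which the table defers contradicts itself in the next bullet.

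A reader might infer that a significant excess of serious events could go unreported. The Protocol does not support that. Section 11.8.2 sends all SAEs to the DSMB and the Project Officer semi-annually whether or not a quarterly trigger occurred, 11.7.3 sends deaths to the DSMB within 15 calendar days, and 11.8.4 reports the listed transfusion reactions semi-annually regardless of incidence.

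**Conclusion.** The mismatch is real, and it sits in an operative safety rule. Read literally, Table 11.3 can block a quarterly SAE alert that 11.8.2 would issue. The consequence is delay, not loss: a non-fatal signal blocked at a quarterly look would reach the DSMB in the next semi-annual report, about three months later if the two schedules run from the same start.

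Even that delay requires the SDMC to follow the table rather than the reporting bullet, and AEs to be very common in both arms. In the simulation the blocked share is at most about 5% when non-serious AEs affect half the patients or fewer, a fifth to a quarter at 80%, and above half only at 95% or more. These percentages illustrate assumed rates and do not estimate what this trial would see. They also treat SAEs as one table. If the AE rate were read within a single MedDRA class, AEs would have to be that common within the class. The point is a small correction that should be made, not a flaw in the choice of test.

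**What to change.** In the quarterly SAE cell of both printings of Table 11.3 (sections 11.8.6 and 11.9.1), change AE rate to SAE rate. Leave the AE row as it is.

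In the same edit, reconcile the 11.8.2 bullet that withholds a report when the Fisher p-value is below the critical value with the reporting bullet above it. Changing the table alone would align it with a section that still gives two opposite instructions. After both changes, the text and the table should state one alert rule.

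The cost is a wording change in two table cells and one bullet, with no new data, test or analysis.
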